8.6.5. Final quality control

A final quality control shall be performed on a sample of $\sqrt{n} + 1$ randomly drawn patients. This quality control shall be conducted in accordance with Pfizer's "CRF to database - QC guideline". The accepted error rate is of 0.5%. A new sample will be collected if the calculated rate exceeds this threshold value. The CRO will draft an overview of this quality control and submit it to Pfizer for review.

8.6.6. Database freeze

The database will only be frozen once the CRO has finished input, data control and possible coding. The database will be frozen in accordance with Pfizer's CT24 procedure. After validation by Pfizer, the database will be frozen by the CRO and made ready for statistical analysis.

8.6.7. Data management report

A data management report will be produced by the CRO and transmitted to Pfizer after freezing the database.

8.6.8. Data transfer

There will be no intermediate partial database transfer. At the end of the project, all paper and electronic documentation (database, programs and documents) will be transferred to Pfizer on CD-ROM.

8.7. Statistical analysis

A detailed statistical analysis plan will be drafted and submitted to the Scientific Committee members for validation before any analyses are performed.

Data for patients included in the standard follow-up group preceding amendment no. 3 will be subject to descriptive statistical analysis with respect to demographic, treatment plan and observed adverse event data.

8.7.1. Analysis strategy

The main analysis will be performed on the population of patients treated with sunitinib, taking into account all grade 3 or 4 AEs observed. Sensitivity analyses will be conducted:

- **using the "missing=failure" strategy**

Any missing values will be replaced by the value corresponding to failure, i.e. grade 3 or 4 AE. For the main outcome measure analysis, this implies that the patient shall be considered as being in a situation of failure.

- **on a population of treated patients compliant with the procedure**

The choice of a compliance threshold upon intervention must be defined in the detailed statistical analysis plan and before the final analysis is performed. This threshold shall consist in a minimum number of successful calls out of the theoretical total number of 14 calls over the entire follow-up period.

8.7.2. Statistical methods used

The descriptive analysis of qualitative and ordinal variables shall include the size and frequency of each modality, with its 95% confidence interval, along with the number of missing data.

Quantitative variables will be described in table form, displaying population size, mean and median, standard deviation, confidence interval, along with the number of missing data.

The profile of drop-out patients shall be compared to that of non-drop-out patients based on the available sociodemographic and clinical variables.

Wherever possible, the analyses will be combined with a graphical representation.

8.7.3. Analysis plan

Main outcome measure analysis

The proportion of patients presenting with at least one grade 3 or 4 AE (whether associated with sunitinib or not) shall be estimated in the overall population of patients treated with sunitinib. A 95% confidence interval will be associated with the observed proportion, using the asymptotic method, or the Clopper-Pearson exact method.

Analysis of secondary outcome measures

The analysis of secondary objectives shall be detailed in the statistical analysis plan.

8.7.4. Study report

The results will be presented in a study report. This study report will accurately and exhaustively summarise the study objectives, methods, results and their interpretation. It shall be reviewed and validated by the scientific committee. Any changes made to the statistical methods must be reported and documented in the clinical/statistical report.

A summary version of the final report will be sent to each participating physician after validation of results by the Scientific Committee.

8.8. Quality Control

During the study, Pfizer, via its CRAs, may conduct periodic monitoring visits to ensure that compliance with the protocol and with good epidemiological practice (GEP). The CRAs may examine the source documents to confirm that the data recorded on the e-CRF are accurate.

Pfizer may at any time conduct quality assurance audits on the participating physician's premises, or audits at the request of the regulatory authorities.

For the purposes of this inspection, the participating physician will provide direct source document access to the CRAs, auditors, or representatives of the competent regulatory authorities.

It is important that the participating physician and concerned staff be available during these visits and during any audits or inspections, and that a sufficient amount of time be dedicated to the process.

8.9. Study limitations

8.8.1 Selection bias

All eligible patients will be invited to take part in the study until the inclusion number is reached, in order to limit the selection of a patient profile for participation in the study.

8.8.2 Measurement bias

Upon set-up, the participating physicians will be asked not to change their patient management practices in any way during the consultations, to avoid creating a "study effect" frequently observed in studies measuring the impact of a procedure. The risk could be of more supportive management (in terms of patient follow-up) of patients, in order to provide them with the information that they would otherwise not receive in the context of the study. This effect, even though it may exist, is considered to be negligible.

The study's main outcome measure concerns grade 3 and 4 adverse events (very severe) that have the greatest impact on patients. While it is expected that patient management via the therapy management platform will globally increase the volume of events reported (more frequent contact with the patient), the hypothesis put forward is that the most severe events will be reduced by early intervention. It is therefore not expected that the double reporting of events by the physicians and nurses will have an effect on the occurrence and reporting of grade 3 and 4 adverse events in the intervention group.

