8.2. Methods

Patients meeting the inclusion and non-inclusion criteria shall be offered to take part in the RENACALL study.

Patient therapeutic management within the establishment must not be modified during the study and must conform to the SPC recommendations. Additionally, patients will receive supplementary follow-up by the call centre.

The RENACALL study aims to evaluate real life patient management.

Email sent to all selected centres to ascertain project feasibility at each centre

Proposal of 10 to 20 oncology centres likely to take part in the study

Centres contacted by email with study participation proposal

Validation of study agreements and transmission of e-CRF identifiers

Patient information and signing of the patient consent form
Completion of the contact form

Inclusion visit

Phone calls as per agreed scheme (figure 2)

Follow-up visit at end of cycles 1, 2 and 4

Figure 1. General study organisation

The patients included in the study will benefit from standard follow-up plus follow-up by a therapy management platform. Platform follow-up shall consist in regular phone calls (see Figure 2) to accompany patients in their real life home management of their treatment with sunitinib (prevention, advice and guidance of patients towards options).

[figure not shown]

Figure 2. Phone call scheme

The study data shall be collected via an electronic case report form:

- By the physician during the inclusion and follow-up visits at the hospital,
- By the therapy management platform nurses during the phone calls. They will have special user profile access to pre-fill the data collected during the phone calls.
- The physicians will have access to the data and reports filled in by the nurses during the phone calls.

The period for patient inclusion into the study is of 22 months. Patients shall be monitored during the first 4 cycles of sunitinib treatment, i.e. for approximately 6 months (1 treatment cycle lasts 6 weeks).

Follow-up visits shall be conducted for all study patients according to standard patient follow-up, i.e. approximately at the end of cycles 1, 2 and 4, during routine patient consultations at the centres (at approximately W6, W12 and W24).

At the end of follow-up, the patients will be asked to fill in a platform satisfaction questionnaire. The participating physicians will be asked to fill in this satisfaction questionnaire at the end of the study.

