The therapy management platform will be managed via a call centre using a CATI (Computer-Assisted Telephone Interview) system. This system is used to instantly enter into the computer all the data collected in response to specific questionnaires submitted by the nurses during the telephone calls, in the context of follow-up.

Patient management varies widely according to the physician and his/her patients' needs. To avoid interfering in follow-up practices, each physician shall follow up their own patients according to their usual practices.

Population of participating physicians

The study shall be proposed to 58 physicians at 50 oncology centres in metropolitan France caring for patients suffering from metastatic/advanced renal cell carcinoma.

Each physician shall be questioned concerning the annual number of patients meeting the inclusion and non-inclusion criteria. It shall also be questioned concerning the systems in place in their centre.

Thus, each centre receiving at least 10 patients per year and that does not already possess a coordinating nurse or platform for routine patient follow-up may be selected to take part in this project, forming the list of identified physicians.

This step, conducted upstream of the study, will allow the identification of 20 to 25 physicians eligible to take part in the study.

A description of the sample of centres shall be provided subsequently, based on the identification data of the participating physicians from each centre (age, gender, geographical situation, etc.). We shall then check that the sample of participating physicians is representative of oncologists in France in terms of centre size and type, in order to guarantee external study validity.

The patients included in the RENACALL study will be monitored not only in the standard manner, but also via the therapy management platform. In the context of standard follow-up, they will be issued the usual logbooks for their treatment, along with any documents routinely used by the centres.

Patient follow-up via a therapy management platform consists in making regular phone calls (14 during the first 4 cycles) to support the patients in the management of their sunitinib treatment.

The calls shall be made from a centralised therapy management platform located in the Paris region, by nurses specifically trained for this role. If necessary, the nurses may be assisted by physicians from the platform.

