The aim of these calls is to support the patients in the management of their treatment by listening to and advising them, implementing preventive measure and taking actions when deemed necessary; the purpose of these calls is to support patients in the management of their sunitinib treatment.

Call frequency is presented in the following figure:

[figure not shown]

Figure 3. Call frequency

The chosen rate is of:

- For the first two cycles, C1 and C2: 5 calls during the first 5 weeks of each cycle (no call during week 6 as the patients are usually seen in consultation),
- For cycles 3 and 4: 2 calls per cycle on weeks 2 and 4.
(decision by the CS not to make calls on weeks 1, 3 and 5).

These calls will be made for patients treated with Sutent®; in the event of termination of treatment during the follow-up period, the call following termination will close the intervention. In the event of cycle start postponement, the first call made shall be postponed to match the expected organisation (cycles 1 and 2: first call during week 1 of the cycle; cycles 3 and 4: first call during week 2 of the cycle).

Call organisation has been defined in collaboration with the concerned healthcare professionals and based on prior experience of therapy management in oncology. It shall be as follows:

- build the patient's trust by covering various aspects of the disease and/or of side effects;
- patient education to avoid serious adverse events (e.g.: dietary advice, sports exercises, etc.);
- guidance and advice when deemed necessary; for example, this may be to:
 - advise the patient to take medicinal products prescribed upstream by his/her physician,
 - guide the patient towards his/her oncologist or general practitioner or other.

The patients will also be able to contact the call centre nurses at any time during the study. A specific module will enable the nurse to record this type of "unscheduled" call.

The platform will also play a coordination role between patients and healthcare professionals, through the following actions:

- Draw up a call report on the e-CRF. This latter shall include the number of successful calls, along with the actions performed by the call centre for each call, such as: no special action, or self-medication, or consultation request to one of the physicians;

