(list choice)	--/--/(DD/MM/YYYY)	 Non-serious  Serious If serious, severity criteria (several possible answers):  Caused death If death, specify: Date of death: --/--/(DD/MM/YYYY) Cause of death: ___  Life-threatening  Hospitalization / prolonged hospitalization  Permanent or major invalidity or disability  Anomaly / congenital malformation  Medically significant event	 Grade 0  Grade 1  Grade 2  Grade 3  Grade 4	 Does not affect daily life  Makes certain actions difficult to accomplish  Affect activities of daily life	 Related to taking Sutent®  Related to a concomitant medicine; Specify the treatment: ___	 Recovered If recovered, recovery date: --/--/(DD/MM/YYYY)  Recovered with sequelae If recovered, recovery date: --/--/(DD/MM/YYYY)  Recovering  Not recovered  Unknown	 Prescription of a treatment, specify:  Medical consultation (general practitioner, specialist, emergency department)  Hospitalisation.  Nurse's advice, specify: ___  Other, specify: ___  Not	 Interruption (temporary, permanent, or delayed)  Dose reduction  Dose increase  Dose unchanged  Unknown  Not applicable

							applicable	
--	--	--	--	--	--	--	------------	--

Instruction: for all current AEs, check AE outcome. If the AE is unresolved, a new row will be generated and linked to the source row. AEs reported by the physicians via the e-CRF are distinguished from AEs reported by the nurses using CATI.

D.5. New AE collection

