8.2.4. Analysis of the primary end point

Analysis population: Safety population

The proportion of patients with at least one grade 3 or 4 AE whether or not related to sunitinib, will be estimated.

All of the grades 3 or 4 AEs defined by the 'Common Terminology Criteria for Adverse Events' (CTCAE v4.03 of June 2010), whether or not related to sunitinib, will be included when these occur during the study follow-up period (up to the end of the 4th treatment cycle or until the treatment is stopped if it is discontinued in the 1st, 2nd or 3rd cycle). All of the AEs will be included whether these are declared by the doctor or by the nurse.

The analyses will be performed both on an overall basis and according to the number of calls made by the call center.

Sensitivity analyses:

The sensitivity analyses will be performed:

- Sensitivity to duration of patient treatment: the results will also be expressed as standardized grade 3 or 4 AE rates developed by the patient and reported over the 6 months of treatment. These rates will be defined by each patient as the number of events which occurred/number of treatment months with sunitinib/ 6).

Secondary analysis:

- **The incidence of the main grade 3 or 4 AEs, whether or not related to sunitinib,** will also be presented in these patients according to the MedDRA SOC (System Organ Class) and PT (Preferred Term) classification. Only categories involving at least 2% of patients will be presented.

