9.4. Analysis of the primary end point

Table 30: Development of AEs during the follow-up period (safety population)

		Number of calls received < xx (N=xxx)	Number of calls received ≥ xx (N=xxx)	Call center (N=xxx)
At least 1 grade 3 or 4 AE whether or not related to Sunitinib	Yes	xx (xx%) [xx; xx]	xx (xx%) [xx; xx]	xx (xx%) [xx; xx]
	No	xx (xx%)	xx (xx%)	xx (xx%)
Number of grade 3 or grade 4 AEs, whether or not related to Sunitinib per patient	Number analyzed	xxx	xxx	xxx
	Mean (±SD)	xx (± xx)	xx (± xx)	xx (± xx)
	Median	xx	xx	xx
	Min-Max	xx - xx	xx - xx	xx - xx
Standardized grade 3 or 4 AEs, whether or not related to Sunitinib per patient, reported over the 6 months of treatment	Number analyzed	xxx	xxx	xxx
	Mean (±SD)	xx (± xx)	xx (± xx)	xx (± xx)
	Median	xx	xx	xx
	Min-Max	xx - xx	xx - xx	xx - xx

Table 31: Description of grade 3 and 4 AEs related or unrelated to sunitinib recorded during the follow-up period (safety population)

		Number of calls received < xx (N=xxx)	Number of calls received ≥ xx (N=xxx)	Call center (N=xxx)
Type of grade 3 or 4 AEs, whether or not related to Sunitinib (SOC – MedDRA category)*	xxxx	xx (xx%)	xx (xx%)	xx (xx%)
	xxxx	xx (xx%)	xx (xx%)	xx (xx%)
	xxxx	xx (xx%)	xx (xx%)	xx (xx%)
Type of grade 3 or 4 AEs, whether or not related to Sunitinib (PT – MedDRA category)*	xxxx	xx (xx%)	xx (xx%)	xx (xx%)
	xxxx	xx (xx%)	xx (xx%)	xx (xx%)
	xxxx	xx (xx%)	xx (xx%)	xx (xx%)

* Categories involving at least 2% of patients

These tables are described for patients under standard follow-up also for exploratory purposes.

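### Grade 3–4 AEs are sought more often in call-centre patients than under standard follow-up, and the plan pools both reporters and dismisses the detection effect with an argument about occurrence

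*Protocol*

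**What the plan says.** Protocol 8.8.2 expects more frequent contact to raise the number of AEs reported overall. It puts forward the hypothesis that early intervention will reduce the most severe events, and for grade 3–4 events among platform patients it concludes: "It is therefore not expected that the double reporting of events by the physicians and nurses will have an effect on the occurrence and reporting".

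Protocol 8.2 describes the intervention as "regular phone calls (14 during the first 4 cycles) to support the patients in the management of their sunitinib treatment". In cycles 1 and 2 there are "5 calls during the first 5 weeks of each cycle"; the later schedule is "For cycles 3 and 4: 2 calls per cycle on weeks 2 and 4". Physician visits take place "approximately at the end of cycles 1, 2 and 4, during routine patient consultations at the centres".

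For the primary endpoint, SAP 8.2.4 states: "All of the AEs will be included whether these are declared by the doctor or by the nurse". Protocol 7.3.1 says that the nurse may propose a grade and that the physician assigns the definitive one.

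The reporter can be identified. Protocol Appendix 7 says of the AE table that "AEs reported by the physicians via the e-CRF are distinguished from AEs reported by the nurses using CATI".

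The result has possible comparators. After Tables 30 and 31, SAP 9.4 adds: "These tables are described for patients under standard follow-up also for exploratory purposes". Table 60 gives the same proportion for standard follow-up patients, and SAP section 3 allows discussion against the SANTORIN cohort.

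**The concern.** The argument in 8.8.2 does not reach its conclusion. A hoped-for fall in the number of severe events cannot show that each severe event is as likely to be recorded with calls as without them. The protocol accepts a detection effect for AEs in general and exempts grade 3–4 AEs on the strength of the effect under study.

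The primary objective is the impact of the platform. A proportion from a single group speaks to impact only beside a reference, whether that is Table 60, SANTORIN or the split by calls received. If calls both reduce severe events and reveal more of them, the two effects pull the pooled proportion in opposite directions and cannot be separated. A real reduction could be hidden, or a rise misread as harm.

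**Working it through.** **1. Contacts by design.** Calls: 5 + 5 + 2 + 2 = 14. Visits: 3 (about W6, W12 and W24). Call-centre patients therefore have 14 + 3 = 17 scheduled contacts at which AEs are collected, against 3 under standard follow-up. SAP Table 8 shows a dash for number of calls in the standard column. Calls are 14/17 = 82% of contacts. That describes opportunity, not the share of AEs found.

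**2. What happens at a call.** Section D.5 of Appendix 7 has the nurse check for AEs the patient has not yet mentioned. The grading table there also raises a proposed grade on context; for example, hypertension moves from grade 2 to grade 3 with a single kidney or existing heart disease. It therefore matters whose grade enters the endpoint. Protocol 7.3.1 says the physician's. SAP 8.2.4 counts nurse-declared AEs without saying so.

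**3. Planned sensitivity analyses.** Protocol 8.7.1 lists missing = failure and a population compliant with the calls. SAP 8.2.4 lists standardisation for treatment duration. None is by reporter.

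**4. The split by calls received.** This does not isolate detection. More calls give more chances to record an event, and they also reflect longer treatment, because calls end after sunitinib is stopped (Protocol 8.2).

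**5. The plan's precision figure.** Half-width = 1.96 × √(p(1 − p)/n). With p = 0.50 and n = 100 this gives 9.8 points, as stated in Protocol 8.5. With p = 0.58 it is 1.96 × √(0.58 × 0.42/100) = 9.7 points. Both cover sampling error in one proportion only.

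**6. Illustration of size.** The documents give no detection rates, so the capture values below are assumptions. The 58% quoted for SANTORIN in Protocol 6.1.2 serves only as a numerical base for what physicians alone might record.

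(a) Suppose calls reveal a grade 3–4 AE in a fraction d of the other 42%. The recorded proportion is 58 + 42d.

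| d | Recorded | Shift (points) |
|---|---|---|
| 5% | 60.1% | 2.1 |
| 10% | 62.2% | 4.2 |
| 20% | 66.4% | 8.4 |
| 30% | 70.6% | 12.6 |

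The shift equals the half-width at d = 9.7/42 ≈ 23%.

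(b) Suppose physicians alone record a share s of affected patients, while calls plus visits record all of them. With no true effect, the recorded proportion is 58/s.

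| s | Recorded | Shift (points) |
|---|---|---|
| 95% | 61.1% | 3.1 |
| 90% | 64.4% | 6.4 |
| 85% | 68.2% | 10.2 |
| 80% | 72.5% | 14.5 |

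A true relative reduction of 1 − s would be hidden exactly. At s = 90%, 64.4% × 0.90 = 58.0%.

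**The case against.** The best defence is that physician recording is thorough and controls the grade. Each visit covers the whole interval since the last one, with a checklist by organ class and number of episodes (CRF 3.4), haematology and biochemistry (CRF 3.3), and interim consultations and hospitalisations (CRF 3.7). Two of the five main grade 3 events listed in Protocol 6.1.2, neutropenia and anaemia, are laboratory findings that need not depend on a call. Nurse grades are only proposals. The analysis is descriptive, no test is planned (SAP 4.1), and the SANTORIN discussion is optional.

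All of this stands as a limit on size. It does not remove the bias, because the physician also grades events that only a call brought to light, and a descriptive comparison is still read as a comparison.

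A reader might infer more than the documents support:

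- **That the proportion is inflated, or that nurses are the main detector.** Only contact counts support this. The net difference from any reference could go either way, since the platform may lower true events and observation periods may differ.
- **That SANTORIN rates are physician-only.** The documents do not say how that cohort collected AEs. The premise holds only for the internal standard follow-up patients.
- **That the physician-first figure is the fair one to compare.** Calls in weeks 1–5 come before the W6 visit, so nurses will often log events that the physician would have found unaided. Those events drop out of a physician-first count, which may then lie well below the physician-only rate and make the platform look beneficial by construction.

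**Conclusion.** The concern holds in a limited form. Ascertainment of grade 3–4 AEs differs by design between call-centre and standard follow-up patients, and the statement in Protocol 8.8.2 does not deal with it. The probable direction is upward for call-centre patients. The size is unknown: the illustrative shifts of about 2 to 14.5 points rest on assumed capture rates and on 58% as a base, and show only that the effect could be comparable with the 9.7-point half-width. The pooled proportion remains a valid description of what was recorded. What it lacks is an indication of how much depends on the calls.

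**What to change.** In SAP 8.2.4 and Table 30, keep the pooled proportion as primary and add two rows:

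- the proportion of patients with a grade 3–4 AE first recorded by the physician;
- the number of patients whose only grade 3–4 AE was first reported by a nurse.

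Define *first recorded* for linked rows (Appendix 7 generates a new row for an unresolved AE) and for events logged at one grade and regraded later. State that the physician's definitive grade counts, so that SAP 8.2.4 agrees with Protocol 7.3.1.

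Present the pooled and physician-first proportions as upper and lower bounds on what physician-only recording would have shown in these patients. Do not substitute the second for the first. Note that the lower bound assumes call reports did not prompt physicians to record further events themselves.

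State the differential-detection limitation wherever the result is set beside Table 60, SANTORIN or the split by calls received. Withdraw the 8.8.2 expectation in the SAP and study report. Amending the protocol itself would achieve little, since data collection was scheduled to end in November 2018 and the SAP is dated 06/02/2019.

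The cost is two rows and some text, with no new data collection. Confirm first that the reporter field, described only as a call-system instruction, is present in the analysis dataset. The drawback is that the bracket may be wide.
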